### AF03

Over 1500 people have been evaluated in clinical trials conducted in the European Union and the US evaluating inactivated, monovalent H5N1 or H1N1 influenza vaccine adjuvanted with AF03. (SP AF03 IB)

In Phase I and Phase II clinical trials in adults, the most frequently observed local reactions were pain, induration and erythema and the most frequently reported solicited systemic reactions in all groups and for each injection were headache and myalgia. Most local and systemic reactions generally appeared on the day following vaccination and disappeared within 3 days without medication use. The addition of AF03 has been associated with a higher incidence of local reactions, mainly characterized by injection site pain and induration, compared to non-adjuvanted vaccine. The addition of AF03 was associated with an increased incidence of systemic reactions when compared to unadjuvanted vaccine in adults.

Some systemic adverse events have been rarely observed concomitantly with the administration of vaccines from other manufacturers containing oil-in-water adjuvants similar to AF03. These systemic adverse events include autoimmune diseases and demyelinating neurological disorders. No causal relationship has been established between these observations and oil-in-water adjuvants. To date, these events have not been observed with AF03 adjuvanted vaccines.

Animal toxicology studies following administration of high doses of AF03 and AF04 have shown increased single cell apoptosis or necrosis in acinar tissues including the lacrimal gland

and the exocrine pancreas in the rabbit model and the parotid glands in rats. These findings were observed only at high doses, of low severity and reversible, they were therefore not considered clinically significant.

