### 11.4.2 Subject Enrollment and Follow-up

Based on the accrual rates observed in similar studies, it seems reasonable to expect that the participating VTEUs will be able to enroll this trial in a timely fashion. In a previous DMID trial (DMID 15-0064, NCT02624219), 4 VTEUs recruited 275 healthy subjects, 19 to 64 years of age, in 20 weeks. In this trial, approximately 3% of subjects, 19 to 64 years of age, were excluded from the per protocol (PP) analysis for the Day 22 primary immunogenicity outcome either because they were lost-to-follow-up or because they had a protocol deviation requiring their exclusion from the PP analysis. The rate of per protocol exclusions for the Day 29 visit in this protocol is expected to follow a similar trend.

A total of 40 subjects will be enrolled and randomized in each group. Assuming up to 3% drop out by Day 29, it is expected that at least 38 subjects per group will be available for the primary immunogenicity analysis. If Advax-CpG55.2 is not available, the study will proceed only with groups 1, 2, 4 and 5 open for enrollment for the remaining subjects (up to 240 or 60 per group) in groups 1, 2, 4 and 5. In this case, assuming the same dropout rate of 3%, it is expected that at least 58 subjects per group will be available for the primary immunogenicity analysis.

Follow-up will consist of 2 segments. The first encompasses the core data for this trial and will consist of results for all study visits through approximately 28 days after study vaccination. The second segment consists of a 6-month immunogenicity assessment and follow-up safety assessments through approximately 12 months after study vaccination.

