### **11.6.2 Safety Data**

Summaries and analysis of safety data will be presented for the Safety Analysis Population. All summaries and analyses will be presented for all subjects.

Solicited AEs will be summarized by severity after the first study vaccination (1-7 days post study vaccination) and as the maximum severity over all 8 days. Additionally, solicited AEs will be analyzed by taking the most severe response over the follow-up period, dichotomizing into a binary variable (none versus mild, moderate, or severe) and using standard techniques, such as exact confidence intervals, to summarize the proportion of subjects reporting each symptom, any injection site symptom, and any systemic symptom. Summaries of solicited AEs will be presented for the first study vaccination by treatment arm. The proportion of subjects reporting symptoms may be compared between treatment arms using Chi-square or Fisher's exact test. Unsolicited AEs will be coded by Medical Dictionary for Regulatory Activities (MedDRA®) for preferred term and system organ class (SOC). The numbers of SAEs and AESIs (including Protocol Specified AESIs, MAAEs, NOCMCs and PIMMCs) are likely to be small in this trial and will be reported by detailed listings showing the event description, MedDRA® preferred term and SOC, relevant dates (study vaccinations and AEs), severity, relatedness, and outcome for each event. Non-serious unsolicited AEs will be summarized as number and percentage of subjects reporting at least one event in each MedDRA® preferred term and SOC, cross tabulated by severity and relationship to study product. Additionally, the proportion of subjects and exact 95% confidence intervals of AEs in aggregate and by MedDRA® categories will be computed. Clinical laboratory data will be summarized by severity for each visit and as the maximum over all post-study vaccination visits. Graphical presentations may include box plots.

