5. SAMPLE SIZE CONSIDERATIONS

This study is planned to enroll a total of 40 subjects in each group. This study is not designed to test a formal null hypothesis. Rather, it is intended to obtain sufficient data to obtain meaningful estimates of the immune response and to uncover any safety issues that occur at a sufficiently high rate that they might be observed in a study of this size. As such, the type one error rate, $\alpha = 0.05$, is not adjusted for multiple comparisons. While this study is not designed to test any specific null hypothesis, the following tables illustrate the precision and power that is available for select estimates and comparisons of interest.

[Table 3](#) indicates the probability of observing one or more safety events, such as solicited injection site or systemic reactogenicity events or an unsolicited non-serious AE of a particular type for sentinel subjects (N=4 or 6), for a single adjuvanted/ unadjuvanted study arm/stratum (N = 40 or 60), for all subjects receiving the same seasonal QIV (N= 120), for all subjects in the trial (N=240).

Binomial confidence intervals (CI) are widest (have the least precision) when the response rate is 50%.

[Table 4](#) is presented to indicate the worst-case scenario for precision of observed exact (Clopper-Pearson) binomial confidence intervals.

[Table 5](#) illustrates the minimum detectable differences in the proportion of subjects responding (e.g., attaining seroconversion or a titer $\geq 1:40$) between two adjuvanted study arms using a two-sided Likelihood Ratio Test and $\alpha = 0.05$.

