9.3.1. Solicited Events and Symptoms

Systemic solicited adverse events were collected pre-vaccination, and systemic and local solicited adverse events were collected at-least 20 minutes post-vaccination and then daily for 7 days after the first study vaccination and graded on a scale of 0 (none), 1 (mild), 2 (moderate) and 3 (severe). Systemic events include fever, feverishness, fatigue, malaise, myalgia, arthralgia, headache, and nausea. Local events include pruritus, ecchymosis, erythema, induration/swelling, pain, and tenderness. Ecchymosis, erythema, and induration are measured by both functional and measurement grading scales as defined in [Table 7](#). The grading scale for systemic events, including quantitative grading for fever, is included in [Table 8](#).

When calculating the incidence of solicited events, each subject will be counted once at the highest severity following the applicable vaccination, and any repetitions will be ignored. For summaries presented for the first study vaccination, the denominator for percentages will be the number of subjects who received the first study vaccination with non-missing data for the event summarized.

The number and percentage of subjects reporting at least one solicited adverse event of each severity will be summarized for each solicited symptom, any systemic symptom, any local symptom, and any symptoms. For each event the denominator is the number of subjects who received the first study vaccination with non-missing data for the specific event. The 95% CI calculated using Clopper-Pearson methodology from a binomial distribution (SAS Proc Freq with a binomial option) will be presented ([Table 119](#)). Logistic regression models will be fit to estimate the effect of study arm on the probability of reporting any local event or reporting any systemic event ([Table 120](#), [Table 121](#)). If statistically significant effects are observed in the model for local events or systemic events, then additional models may be fit for each individual event of that type.

$$\text{logit}[P(\text{Event})] = \beta_0 + \beta_1 \times \text{Treatment} + \varepsilon,$$

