12. SUMMARY OF CHANGES IN THE CONDUCT OF THE STUDY OR PLANNED ANALYSES

This SAP includes one change from the analyses described in the protocol. Logistic regression will be used instead of the Chi-Square or Fisher's exact test to model the relationship of treatment with reporting any local or systemic events post vaccination. Besides providing the strength of the association between the treatment and probability of reporting any local or systemic event in terms of odds ratio, logistic regression also provides a prediction model for the probability of a local or solicited event occurring given the subject's study arm. Version 3.0 of the SAP includes moving Day 180 and Day 365 immunogenicity endpoints from secondary to exploratory endpoints and the addition of a topline report.

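### The logistic regression for solicited events (SAP 9.3.1, Tables 120 and 121) names no estimator, test or rule for an arm at 0% or 100%; the analysis its table layout implies fails in such an arm

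*SAP*

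**What the plan says.** Protocol 11.6.2 left the between-arm comparison of solicited events optional and open to either of two tests: "The proportion of subjects reporting symptoms may be compared between treatment arms using Chi-square or Fisher's exact test".

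SAP section 12 declares a change for solicited events: "Logistic regression will be used instead of the Chi-Square or Fisher's exact test to model the relationship of treatment with reporting any local or systemic". The reasons given are that the model yields an odds ratio and a predicted probability for each arm. SAP 9.3.1 then specifies: "Logistic regression models will be fit to estimate the effect of study arm on the probability of reporting any local event". A second model does the same for systemic events, and study arm is the only term in each. If significant effects are found in a composite model, models for the individual events of that type may follow. The SAP does not say which test decides this.

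The Table 120 shell, which Table 121 follows, has one row per arm with parameter estimate, SE, p-value, odds ratio and 95% CI. Fluzone is the reference. SAP section 11 says only that SAS 9.4 or above will be used. For the Clopper-Pearson intervals, 9.3.1 names the SAS procedure and option; for the logistic model it names none.

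On size, Protocol 11.4.2 states: "A total of 40 subjects will be enrolled and randomized in each group". SAP section 5 adds that the 0.05 type one error rate "is not adjusted for multiple comparisons".

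**The concern.** A logistic model with arm as its only factor has no finite maximum-likelihood estimate for an arm in which every subject, or no subject, has the event (quasi-complete separation). Software stops at an arbitrary large coefficient with an enormous standard error, so the Wald p-value is close to 1 and the interval carries no information. The chi-square and Fisher tests do not break down in this way.

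The setting makes such arms possible. Any local event is a composite of several reactions at any grade, and Protocol 2.3.1 reports that "The addition of AF03 has been associated with a higher incidence of local reactions", so an adjuvanted arm might reach 100%. Rare single events such as fever might be absent from an arm of 40. If the empty arm is the Fluzone reference, all five odds ratios are lost together.

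Reactogenicity is a primary safety outcome, and these models are the only planned between-arm test of it. At stake is a printed odds ratio and p-value that contradict the counts in the neighbouring tables.

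**Working it through.** **Inputs.** From the documents: 40 per arm, six arms, four of them adjuvanted, alpha 0.05 (used two-sided here). Assumed, because the documents give no figure: any-local rates of 80% to 98% in the adjuvanted arms and 1% to 3% for rare single events.

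**The plan's own figure.** Protocol Table 10 (SAP Table 3) gives the chance of seeing at least one event among 40 subjects. The formula 1−(1−p)^40 gives 98.5%, 33.1%, 3.9% and 0.4% at rates of 10%, 1%, 0.1% and 0.01%. The table prints 98, 33, 3 and <1, so it is reproduced, with truncation. Its complement at 1% is a 67% chance of 0/40.

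**Why the Wald test fails.** For a 40/40 arm the fitted logit b grows without limit. The information is about 40·e^(−b), so the SE is about e^(b/2)/√40 and z = b/SE tends to 0. A six-arm fit with 24, 40, 30, 25, 39 and 30 events of 40 (Fluzone first) gave the 40/40 arm a log odds ratio of 17.8 and SE 1418, so z = 0.013 and p = 0.99. For the same contrast, Fisher's p is 4.7×10⁻⁶ and the likelihood-ratio p is 3×10⁻⁷.

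**Two examples.** Fisher's two-sided p with equal arms is 2·C(40,k)/C(80,k), where k is the number in the less frequent category.
- 40/40 v 30/40 (k=10): p = 0.001.
- 6/40 v 0/40 (k=6): p = 0.026.

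Firth's estimate in this saturated model adds 0.5 to each cell.
- 40/40 v 30/40: (40.5/0.5)/(30.5/10.5) = 27.9; penalised likelihood-ratio p = 0.0004.
- 6/40 v 0/40: (6.5/34.5)/(0.5/40.5) = 15.3; penalised likelihood-ratio p = 0.010, profile CI 1.70 to 2017.
- The Firth estimate with a Wald p gives 0.07 for 6/40 v 0/40, so the test must be named as well as the estimator.

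**Contrasts without separation.** For 39/40 v 24/40 the log odds ratio is ln(39/1)−ln(24/16) = 3.26 and the SE is √(1/39+1+1/24+1/16) = 1.06, so Wald p = 0.002. For 39/40 v 20/40, p = 0.0006.

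**Chance of separation, any local event.** One arm reaches 40/40 with probability q = p^40; at least one of four does so with probability 1−(1−q)^4, taking the same rate in all four.
- 80%: q = 0.013%, any of four 0.05%.
- 90%: q = 1.5%, any of four 6%.
- 95%: q = 13%, any of four 42%.
- 98%: q = 45%, any of four 91%.

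In the other direction, 0/40 for a composite with a true rate of 20% or more has probability at most 0.8^40 = 0.013%.

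**Chance of separation, rare single event.** 0/40 in Fluzone: 0.99^40 = 67% at a 1% rate, 0.97^40 = 30% at 3%.

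**How often it changes a result.** The third column is the probability that Fisher gives p<0.05 and the contrast is separated. Wald power counts separation as non-significant.

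| True rates | Fisher power | Wald power | Fisher p<0.05 and separated |
|---|---|---|---|
| 60% v 80% | 0.41 | 0.50 | 0.0% |
| 60% v 90% | 0.85 | 0.88 | 1.5% |
| 60% v 95% | 0.97 | 0.85 | 13% |
| 70% v 98% | 0.94 | 0.51 | 44% |
| 2% v 20% | 0.64 | 0.27 | 37% |

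**Overall test of arm.** With counts 0, 10, 5, 1, 8 and 4 of 40 (Fluzone first), all five contrasts have Wald p about 0.99. The overall Wald p is 0.15, against a likelihood-ratio p of 0.0004.

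**The case against.** The strongest reply is that the SAP does not commit to the failing method. Maximum likelihood and Wald are inferred from the table columns and the absence of any other instruction; a likelihood-ratio, exact or penalised analysis would not fail. That is right, and the fault is one of specification. It is still more than missing detail, because running the shells with ordinary settings would print the misleading row.

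It can also be said that little depends on these p-values. Tables 119 and 122 give exact per-arm intervals: 40/40 appears as 91.2% to 100% and 24/40 as 43.3% to 75.1%. The trial disclaims formal hypothesis testing (SAP 6.8). The halting rules in Protocol 9.5.2 use counts and events. Tables 120 and 121 are not marked for the expedited report. All of this stands. It limits the consequence but does not justify a p-value near 1 beside 40/40 v 30/40.

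A reader might infer more than the documents support:
- *That a required exact test was dropped.* The protocol's comparison was optional and allowed chi-square as well as Fisher, and the SAP declared the change with reasons.
- *That separation is likely for any local event because adjuvanted rates are near 100%.* Protocol 2.3.1 reports higher incidence but gives no any-local rate; at 80% to 90% the problem is rare.
- *That the individual-event models would be blocked.* One 40/40 adjuvanted arm leaves the other four contrasts intact, and any of them may supply the significant effect. Losing all five needs the reference arm at 0% or 100%; for a composite at 20% or more, 0/40 is practically excluded.

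**Conclusion.** The point holds as a gap in specification with a conditional failure. Under the maximum-likelihood and Wald analysis that the Table 120 layout suggests, every contrast involving a 0/40 or 40/40 arm loses its odds ratio, interval and p-value. It would be wrong to conclude that the largest reactogenicity differences will generally come out non-significant: unseparated differences as large as 39/40 v 20/40 are handled properly, and at 60% v 90% Wald power slightly exceeds Fisher power.

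For the two pre-specified composites, the risk matters only if true adjuvanted rates are about 95% or more, which the documents neither state nor exclude. The optional individual-event models are more exposed, since an empty Fluzone arm is common for events at 1% to 3%. Even there, inference is harmed only when another arm differs materially; Fisher's test itself needs about 6/40 against 0/40 to reach p=0.026.

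The change should be made before Tables 120 and 121 are run. The trial's safety monitoring and its per-arm descriptive results do not depend on it.

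**What to change.** In SAP 9.3.1 and the shells for Tables 120 and 121, specify Firth-penalised logistic regression (the FIRTH option of PROC LOGISTIC) with profile penalised-likelihood 95% CIs and penalised likelihood-ratio p-values, explicitly not Wald. Exact logistic regression is an acceptable alternative. Apply the choice to the composite and the individual-event models alike. State that the step from a composite to its individual events depends on the likelihood-ratio test of study arm.

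The cost is a software option, a few sentences in the SAP and relabelled p-value and CI columns in the shells. Penalised odds ratios are shrunk slightly.

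Two further edits are separate from this point. The additive error term in the model formula should be deleted as a clerical correction. A column for the difference in percentages with its 95% CI would help readers but is optional.

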For each systemic and local event, any systemic event, any local event, and any solicited event, the maximum severity over 7 days after the first study vaccination will be summarized for the Safety Population. The number and percentage of subjects reporting each event will be summarized by the maximum severity and study arm. For each event the denominator is the number of subjects who received the first study vaccination with non-missing data for the specific event. The 95% CI calculated using Clopper-Pearson methodology from a binomial distribution (SAS Proc Freq with a binomial option) will be presented ([Table 122](#)).

The number of subjects reporting a solicited adverse event will be summarized for each day post the first study vaccination combined both in a summary table ([Table 123](#)) and graphically in a bar chart ([Figure 96](#) and [Figure 97](#)).

Systemic and Local solicited events reported by subject will be presented in [Listing 20](#) and [Listing 21](#), sorted by subject ID, vaccination number, parameter, and study day.

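### The only planned between-arm models of reactogenicity ignore severity grade, and individual-symptom models depend on significance of the any-event composites

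*SAP*

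**What the plan says.** SAP 9.3.1 has solicited events "graded on a scale of 0 (none), 1 (mild), 2 (moderate) and 3 (severe"). It then fits logistic models to "estimate the effect of study arm on the probability of reporting any local event or reporting any systemic event" (Tables 120 and 121). Protocol 11.6.2 defines the split: the worst response is taken, "dichotomizing into a binary variable (none versus mild, moderate, or severe").

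The next sentence of SAP 9.3.1 sets the condition for going further: "If statistically significant effects are observed in the model for local events or systemic events, then additional models may be fit for each individual event". It does not name the test, the contrast or the level that counts as significant.

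The protocol set no such condition: "The proportion of subjects reporting symptoms may be compared between treatment arms using Chi-square or Fisher's exact test". SAP Section 12 records the change of method, "Logistic regression will be used instead of the Chi-Square or Fisher's exact test", and gives reasons for it, but none for the condition.

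Outside the models, and unconditionally, counts and percentages with exact 95% CIs "will be summarized for each solicited symptom, any systemic symptom, any local symptom, and any symptoms" (Table 119). Table 122 keeps the grade: "The number and percentage of subjects reporting each event will be summarized by the maximum severity and study arm".

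**The concern.** Reactogenicity is a primary safety objective, and a central question about an adjuvant is how far it moves reactions from mild to moderate or severe. In Tables 120 and 121 a subject with mild tenderness counts the same as one with a grade 3 reaction, so a severity shift among subjects who would have reacted anyway contributes nothing to the estimate.

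The condition adds a second loss. Protocol 2.3.1 describes the local effect of AF03 mainly as pain and induration, which are individual symptoms. A composite of six local or eight systemic symptoms dilutes a change in one of them, and the symptom-level comparison is then left unplanned. This also sits oddly with SAP Sections 5 and 6.8, which say that the study tests no specific null hypothesis and makes no multiplicity adjustment. An estimation study has little reason to make estimates depend on a significance test.

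**Working it through.** **Stated figures.** The plan gives no event rate, effect size or power for these models, so there is nothing to reproduce directly. As a check of method, the exact power calculation below was applied to SAP Table 5. It agrees with eleven of the twelve cells. The exception (0.90 with N=38, where even a rise to 1.00 has power 0.746) is a separate matter.

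**Is a ceiling documented?** For systemic events, Protocol 2.3.1 gives rates for the earlier Advax-CpG246.1: headache 20-35%, muscle ache about 20%, fatigue about 10%, chills about 5%.
- The any-systemic rate from these four is at least the largest, 20-35%, and at most the sum, 55-70%.
- Under independence it is 1 − 0.80×0.80×0.90×0.95 = 45% to 1 − 0.65×0.80×0.90×0.95 = 56%.
- Unlisted symptoms could add to this.

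For local events no percentage is given for any arm.

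**Power with 40 per arm, two-sided 0.05.** All grade distributions are assumptions. Binary outcomes use G² = 2 Σ O ln(O/E) > 3.84, with power summed over all pairs (x, y) weighted by Bin(x; 40, p₀) Bin(y; 40, p₁). The ordinal column is the tie-corrected Wilcoxon test on the 0-3 grade (the score-test analogue of proportional odds), simulated; repeat runs agree within a point or two.

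| | None/mild/moderate/severe, % | Any event | Grade ≥2 | Ordinal |
|---|---|---|---|---|
| A | 15/65/18/2 vs 4/52/37/7 | 45% | 66% | 76% |
| B | 10/70/18/2 vs 3/47/42/8 | 32% | 82% | 86% |
| C | 30/55/13/2 vs 20/45/29/6 | 19% | 56% | 48% |
| D | 35/50/13/2 vs 10/55/30/5 | 80% | 56% | 85% |
| E | 60/30/8/2 vs 35/45/17/3 | 64% | 25% | 61% |
| F | 50/38/10/2 vs 20/62/15/3 | 82% | 12% | 72% |

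In A, grade 2 or higher goes from 18+2 = 20% to 37+7 = 44%, and any-versus-none misses it in 100 − 45 = 55% of trials. C shows the same pattern without a ceiling (any event 70% to 80%). D to F are mainly effects on occurrence; there the binary model loses little or is the better one.

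**The condition.** Take the eight systemic symptoms with within-subject latent correlation 0.3 and one two-arm comparison.
- Baseline 10% each, one symptom raised to 40%: any-systemic moves only from 44% to 59%. The composite is significant about 27% of the time, the symptom alone about 91%, both about 26%.
- Baseline 20% each, one raised to 50%: composite 14%, symptom 82%, both 14%.

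The undefined trigger can also err the other way. If it means any of the five arm coefficients in a model at 0.05, it fires under the null with probability about 1 − 0.95⁵ = 23%, or 1 − 0.95¹⁰ = 40% over both models. This treats the coefficients as independent; they share a reference arm.

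**Sparse cells.** If an adjuvanted arm had a true any-local rate of 95%, P(40 of 40) = 0.95⁴⁰ = 13%; at 98% it is 45%. The ordinary logistic odds ratio for that arm is then not estimable.

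**The case against.** The strongest reply is that severity is already reported, and more prominently than the models. Table 117 has separate rows for grade 3 local and grade 3 systemic events. Table 122 gives maximum grade for every symptom and composite, and Table 123 gives grade by day. Tables 117 and 122 are marked for the expedited report; Tables 120 and 121 are not. The halting rules in Protocol 9.5 act on grades directly. All of this stands. A reader might infer that moderate and severe reactions could double unseen, but the documents do not support that: the doubling would show in Table 122. What is missing is an unconditional planned between-arm estimate of severity or of any individual symptom, because Tables 119 and 122 carry single-arm intervals.

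Second, a reader might infer that the composites sit near 100% in every arm. No document says so. The protocol's systemic figures point the other way, and a local ceiling is plausible but assumed. Protocol 2.3.1 describes the AF03 effect as higher incidence, which is the contrast that Tables 120 and 121 estimate. A high rate in the adjuvanted arm alone does not disable the model: with 95% there, any-versus-none power is 0.99 from an unadjuvanted 60%, 0.89 from 70%, 0.58 from 80% and 0.17 from 90%.

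Third, replacing the binary model could lose power, as E and F show. That stands, and is why the ordinal estimate should be added rather than substituted.

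Fourth, the text says that further models may be fit. A reader might infer that a non-significant composite forbids them; it leaves them unplanned, and a significant one does not guarantee them.

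Finally, this is a Phase I estimation study, so power is not the design criterion. True, but the SAP itself makes significance the trigger, so the chance of significance is the relevant measure of that trigger.

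**Conclusion.** The point holds in a limited form. The planned models discard the grade, and symptom-level between-arm estimates depend on an undefined significance trigger that the protocol did not have. The descriptive safety record is intact.

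The size depends on the kind of effect: about 19-45% power against 48-86% for an ordinal test in the severity-shift scenarios (A to C), and no material loss, or a gain of up to about 10 points for the binary model, when the effect is on occurrence (E and F). The 27% against 91% for the condition rests on one symptom changing, latent correlation 0.3, and the trigger being a single two-arm comparison; a different trigger or several symptoms changing would alter it. This is a worthwhile and cheap improvement to a primary safety objective, not a defect that undermines the safety conclusions.

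**What to change.** In SAP 9.3.1 and the shells for Tables 120 and 121:

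- Keep the any-event odds ratio. Beside it, add a proportional-odds estimate (or a grade 2-or-higher odds ratio) on the maximum grade already derived for Table 122.
- Report each adjuvanted arm against its own unadjuvanted vaccine: groups 2 and 3 against 1, groups 5 and 6 against 4. The present shell uses Fluzone as the only reference, so adjuvanted Flublok against Flublok is not shown directly.
- Delete the significance condition. Report between-arm estimates with 95% CIs for every individual symptom whatever the composite shows, labelled descriptive and unadjusted.
- Name exact or Firth estimation for cells of 0/40 or 40/40.
- Record the change in SAP Section 12.

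No new data are needed; the cost is a model statement, a few rows and one further table. The downsides are a proportional-odds assumption, which Table 122 lets readers check; few severe events (2-8% of 40 is about 1 to 3 subjects); and more unadjusted comparisons: (14 symptoms + 2 composites) × 4 contrasts = 64.
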